Clinical Study Protocol

A Randomized, Double-blind, Phase 2, Placebo Controlled Study to Determine the Safety and Efficacy of Ivacaftor (VX-770) for the Treatment of Chronic Obstructive Pulmonary Disease (The Topic Trial)

9/2/2016

Principal Investigators: [name], MSPH

[name]

PROTOCOL SYNOPSIS

Title: A Randomized, Double-blind, Phase 2, Placebo Controlled Study to Determine the Safety and Efficacy of Ivacaftor (VX-770) for the Treatment of Chronic Obstructive Pulmonary Disease (The Topic Trial)

Lead Investigators: [name] MSPH
[name]
[name]
[name]
[contact]
Email: [contact]

[name] MD
[name]
[name]
[name]
[contact]
Email: [contact]

Clinical Phase Phase 2

Study Synopsis

General Description: The study is a Phase 2 Study to establish the safety and efficacy of the CFTR potentiator ivacaftor in patients with chronic obstructive pulmonary disease (COPD), chronic bronchitis, and acquired CFTR dysfunction as detected by sweat chloride analysis. The design is a pilot, randomized (3:1, active:placebo), double-blind, placebo-controlled study to determine the safety and efficacy of ivacaftor (VX-770). Approximately 40 subjects with COPD will be randomized (Figure 1).

Primary Objective:

1. Evaluate the safety of ivacaftor treatment in patients with COPD and chronic bronchitis
2. Evaluate the pharmacokinetics of ivacaftor in patients with COPD and chronic bronchitis

Secondary Objectives:

1. Measure the pharmacodynamics of ivacaftor on CFTR activity (Sweat Chloride, MCC) in COPD patients with chronic bronchitis
2. Measure the effect of ivacaftor treatment on clinical outcomes (spirometry, patient symptoms, 6 minute walk test) in COPD patients with chronic bronchitis

Primary Endpoint:

1. Safety as determined by adverse events, clinical laboratory values (serum chemistry, hematology, coagulation studies), standard digital ECGs, vital signs, and physical examinations

2. Pharmacokinetic parameters of ivacaftor in COPD subjects (8 hr day 1 PK and PK peak and trough concentrations on days 28, and 84. A random PK will be collected on day 56)

Secondary Endpoints:

1. Change in respiratory and peripheral CFTR activity as detected by sweat chloride and MCC respectively
2. Indicators of respiratory function and COPD health (Change in FEV₁% as detected by spirometry, secondary spirometry values (FVC%, FEV₁/FVC), 6 minute walk test
3. Patient reported outcomes (San Diego Shortness of Breath Questionnaire¹, the Breathlessness, Cough, and Sputum Scale (BCSS)^{2,3} the Cough and Sputum Assessment Questionnaire (CASA-Q)^{4,5} and the COPD assessment test (CAT) the St. George Respiratory Questionnaire (SGRQ), and the EXACT-PRO).

[figure not shown]

Fig. 1. Trial Schematic.

Study Population: The study is a Phase 2 Study to establish the safety and efficacy of the CFTR potentiator ivacaftor in patients with chronic obstructive pulmonary disease (COPD), chronic bronchitis, and acquired CFTR dysfunction as detected by sweat chloride analysis. The design is a pilot, randomized (3:1, active:placebo), double-blind, placebo-controlled study to determine the safety and efficacy of ivacaftor (VX-770) in approximately 40 subjects with COPD (Figure 1).

Inclusion Criteria:

- Male or Female age 40-80
- A Clinical diagnosis of COPD as defined by GOLD
- At Least a 10 pack year smoking history
- Exhibit symptoms of chronic bronchitis as defined by the Medical Research Council
- FEV1% predicted $\geq 35\%$ and $\leq 70\%$ Post Bronchodilator
- Clinically stable in the last 4 weeks with no evidence of COPD exacerbation
- Weight of 40 kg-120 kg
- Willingness to use at least one form of acceptable birth control including abstinence, condom with spermicide, or hormonal contraceptives from time of signing ICF through study follow up visit
- Willing to monitor blood glucose if known history of diabetes mellitus requiring insulin or medical therapy
- Element of CFTR Dysfunction, as defined by Sweat Chloride $> 30 \text{ mEq/L}$

Exclusion Criteria

- Current Diagnosis of Asthma
- Known Diagnosis of Cystic Fibrosis
- Daytime use of Oxygen Therapy
- Documented history of drug abuse within the last year
- Subjects should not have a pulmonary exacerbation or changes in therapy for pulmonary disease within 28 days before receiving the first dose of study drug.
- Cirrhosis or elevated liver transaminases $> 3X \text{ ULN}$
- GFR < 50 estimated by Cockroft-Gault
- Any illness or abnormal lab finding that, in the opinion of the investigator might confound the results of the study or pose an additional risk in administering study drug to the subject.
- Pregnant or Breastfeeding
- Subjects taking moderate or strong inhibitors or inducers of CYP3A4, including certain herbal medications and grapefruit juice. (Excluded medications and foods including the drugs and foods listed in the IRB HSP application.)
- Uncontrolled Diabetes
- Recent (e.g 1year) arterial thrombotic events (peripheral arterial disease, thrombotic stroke)
- Clinically significant arrhythmias requiring anti-arrhythmic agent(s) or conduction abnormalities that in the opinion of the investigator that affect patient safety such as the abnormalities listed below (patients with stable coronary artery disease are eligible)
 - ♦ Angina symptoms
 - ♦ History of MI
 - ♦ Revascularization procedure in the last year prior to screening
 - ♦ Clinically significant congestive heart failure (known LVEF $\leq 45\%$, cor pulmonale, diastolic heart failure, etc)

Investigational Drug: Ivacaftor, 150 mg PO every 12 hrs (or matching placebo)

Schedule of Study Visits: The first dose of ivacaftor will be administered at the Day 1 visit. Ivacaftor will be taken twice daily, with 12 hours between each dose from day 1 through the morning dose of day 84. Study visits will occur at Screening (-28 to -1 days), Day 1, Day 28 (\pm 7), Day 56 (\pm 7), Day 84 (\pm 7), and Follow-up (14 \pm 7 days after the last dose of ivacaftor).

Outcome Measures:

Safety assessments: Assessments include tests used in clinical studies to monitor the safety of ivacaftor in CF, including adverse event reporting, clinical laboratory testing, physical exams, and spirometry. The PI will review all SAEs in real time and conduct appropriate reporting to the FDA and IRB, as required, within 24hrs at maximum. Interim safety analysis will include review of AEs and safety labs by the PI and will be conducted after completion of approximately 10, 20, and 30 subjects. Ocular exam will be performed at baseline unless known history of cataracts.

PK: PK/PD analyses between ivacaftor levels and CFTR activity in the sweat gland will reveal new insights into the degree that wild-type CFTR can be activated. Calculated PK parameters include: area-under-the-curve (AUC₁₂), maximum plasma concentration (C_{max}), time to C_{max} (T_{max}), oral clearance (CL/F), terminal apparent distribution volume (V_z/F), and elimination half-life (t_{1/2}). Subsequently, intensive data and sparse plasma concentrations will be combined to create a population PK model to assess covariates, such as age, weight, sex, smoking status, etc. as previously conducted by our group for NIH and industry sponsored studies.

MCC: Clearance of Tc⁹⁹ sulfur colloid is a measure of MCC of the lungs, and is calculated by a standard protocol developed by the Cystic Fibrosis Therapeutics Development Network and in use at our center. The method provides a robust measure of MCC, and has been sensitive to the effects of inhaled pharmacologic agents in CF and COPD including improvements of an unprecedentedly large magnitude in CF patients with the G551D-CFTR mutation treated with ivacaftor measured in a multicenter study. The technique allows estimates of MCC in both the small and large airway compartments.

6 Minute Walk Test: this practical test is commonly used in the assessment of patients with COPD. The 6MWT will be used as a measure of functional status of patients and as a measurement of changes in functional capacity due to the intervention.

CFTR activity in the periphery: Sweat chloride abnormality is correlated with COPD severity and symptoms, and is a highly sensitive outcome measure for CFTR-directed therapeutics. We have shown sweat chloride is sensitive to the presence of cigarette smoking and COPD, and the test has been successfully used as an endpoint in multiple CF trials, including studies to detect the efficacy of ivacaftor therapy.

Spirometry: Spirometry is a standard outcome measure in COPD and a major indicator of efficacy and safety in COPD clinical trials. Post-bronchodilator spirometry will be performed by ATS criteria and percent predicted FEV₁, FVC, and FEF25-75 will be calculated based on Hankinson prediction equations.

Patient Reported Outcomes: Questionnaires designed to detect the burden of cough and sputum symptoms as well as overall health status will be used to monitor clinical outcome before and after study drug. This includes the San Diego Shortness of Breath Questionnaire, the Breathlessness, Cough, and Sputum Scale (BCSS), the Cough and Sputum Assessment

Questionnaire (CASA-Q), the COPD assessment test (CAT), the St. George Respiratory Questionnaire (SGRQ), and the EXACT-PRO (the latter which will be useful to track pulmonary exacerbations).

Biomarker collection: Serum and plasma will be stored with and without protease inhibitors to allow exploratory biomarker studies to be conducted upon conclusion of the study. We anticipate testing for free acrolein since we hypothesize elevated acrolein levels may be associated with CFTR dysfunction. Acrolein will be estimated using our LC/MS/MS protocol.

CFTR Genotyping: CFTR will be sequenced by commercially available procedures as performed by the John Hopkins University Genetics Laboratory. Analysis will be stratified by the presence and absence of CFTR mutations. Since we have a large pool of previously tested COPD patients, we will target our enrollment to those without known CFTR mutations.

Statistical plan: Safety analysis will be conducted by descriptive statistics. Pharmacodynamic analysis will be evaluated within group for the ivacaftor treatment group for changes between screening/day 1 and day 84, in comparison to between group changes in the placebo treatment group. The primary outcome measure is safety; the co-primary efficacy outcome measures are MCC (AUC₆₀) and change in FEV1 (% predicted). Power analysis for measurements of MCC, CFTR function measured by sweat chloride, and FEV1 (% predicted) are provided in below. Secondary outcome measures including change in other measures of spirometry, PROs, exacerbation frequency, and 6MWD will also be analyzed. The off drug effect will be measured by using data from the follow-up visit to assess the change from on drug to washout at the follow up visit.

Role of Vertex IIS:

- Vertex Pharmaceuticals will provide ivacaftor and matching placebo to randomize up to approximately 50 subjects to achieve approximately 40 completers (35 active patients and 15 placebo treated patients for 84 days, assuming 5 dropouts in the ivacaftor group and 5 dropouts in the placebo group). This will provide sufficient compound for lost samples, if they occur.
- To facilitate PK studies planned at UAB, we also request pure ivacaftor powder and stable isotope labeled internal standard for assay development and validation. We request 2-5 mg of each.

1.0 Rationale:

Like CF, COPD is characterized by small airway mucus obstruction that is associated with accelerated loss of lung function and mortality. Our preliminary data indicate that cigarette smoke exerts deleterious effects on airway epithelial function including the reduction of CFTR activity, enhanced mucus expression, and a pronounced reduction in mucociliary transport (MCT)⁶. Preliminary data also indicate that approximately 50% of patients with COPD have reduced CFTR activity, as detected in the upper airways^{6,7}, lower airways⁷ and sweat glands⁸. Furthermore, CFTR dysfunction is independently associated with chronic bronchitis, can persist despite smoking cessation, and can be reversed by the CFTR potentiator ivacaftor (VX-770) in vitro by activating wild-type CFTR, resulting in a robust increase in MCT⁶. Combined with unprecedented clinical improvement via augmented mucociliary clearance in CF patients with a responsive CFTR mutation treated with ivacaftor^{9,10}, these data indicate that CFTR represents a viable therapeutic target to address mucus stasis in a large subset of COPD patients (potentially representing over 4 million patients in the U.S. alone)¹¹. *This project will investigate the hypothesis that ivacaftor can augment CFTR activity in individuals with COPD who exhibit chronic bronchitis, resulting in meaningful improvements in epithelial function and respiratory health.* Our initial pilot study in patients with COPD and chronic bronchitis demonstrated that ivacaftor was safe, demonstrated stable pharmacokinetics, and exhibited a trend towards efficacy in measures of PROs and sweat chloride.¹² The current trial will test the safety, pharmacokinetics, and pharmacodynamics of ivacaftor in a larger number of COPD patients with chronic bronchitis and for a longer treatment period, evaluating the potential of CFTR potentiator therapy to address acquired CFTR dysfunction in this population and set the stage for larger and longer-term trials in the future. Based on an IND already in place in the [name] laboratory, an IRB familiar with the proposed study, an experienced clinical investigation team with expertise in all of the endpoints proposed, and a well characterized COPD population prioritized for the presence chronic bronchitis, CFTR dysfunction, and the absence of congenital CFTR mutations, we are poised to deliver the trial.

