4.0 STUDY DESIGN

The study is a Phase 2 Study to establish the safety and efficacy of the CFTR potentiator ivacaftor in patients with chronic obstructive pulmonary disease (COPD), chronic bronchitis, and acquired CFTR dysfunction as detected by sweat chloride analysis. The design is a pilot, randomized (3:1, active:placebo), double-blind, placebo-controlled study to determine the safety and efficacy of ivacaftor (VX-770) in approximately 40 subjects with COPD.

Enrollment is planned at our single center, The University of Alabama at Birmingham. Patients will be randomized 3:1 to active drug (n=30) and placebo (10) to achieve the enrollment goal.

- A sufficient number of subjects will be screened to randomize up to 50 subjects to achieve 40 completed subjects to receive either ivacaftor 150 mg BID (n=30) or placebo (n=10) for 84 days.
- The schedule of assessments is shown in Table 1. The protocol design is shown in Figure 1.
- Ivacaftor and matching placebo will be orally administered as capsules according to the following guidelines:
 - Between study visit Day 1 and study visit Day 84, subjects will take 1 dose of study drug each day in the morning, beginning any time between 08:00 h (8:00 AM) and 12:00 h (12:00 PM). Whenever possible, subjects should take the study drug at the same time each day.

- On the study visit days when PK samples are collected (study visit Days 1, 28, 56, and 84), the study drug is to be taken by the subject while he/she is at the study site
- For visits after the Day 1 visit, subjects will be instructed to bring all remaining study drug materials to the site; study drug will be dispensed at each visit.
- Ivacaftor will be prepared and dispensed by an unblinded pharmacist.
- Subjects will be instructed to continue their standard COPD medication regimen.

Table 1. Schedule of Assessments ^a8 hr PK (pre, 1, 2, 4, 8, hr samples). ^b peak and trough PK only, ^crandom PK, ^donly if indicated.

Assessment	Screen (Day -28 to -1) Visit 1	Day 1	Day 28 (± 2)	Day 56 (± 2)	Day 84 (± 2)	Follow Up (Day 98 ± 2)
		Visit 2	Visit 3	Visit 4	Visit 5	Visit 6
Informed Consent	X					
Medical History & Concomitant Medications	X	X	X	X	X	X
Physical Examination	X	X	X	X	X	X
Safety Labs	X		X	X	X	X ^d
CFTR Genotyping	X					
Urine Pregnancy Test		X	X	X	X	X
Serum Pregnancy Test	X					
Blood Biomarker Collection		X	X	X	X	X
Spirometry	X	X	X	X	X	X
Sweat Chloride	X	X	X	X	X	X
MCC	X				X	
Patient report outcome questionnaires		X	X	X	X	X

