Table 2. Power and sample size of the proposed study. All calculations are based on within subject changes observed with prior experience (as indicated by references in Table) or preliminary data, n=27 active treatment patients among all doses assignments and accounting for 10% drop-out rate, a two-sided paired t-test, and $\alpha=0.05$. ^aPower=80% between-groups at SD=12.8 mmol/L and 90% at SD=11.1 mmol/L. ^bPower=80% to detect 3.9% change in FEV₁% between groups; this corresponds to 5.1% relative improvement in FEV₁ assuming ~55% FEV₁% predicted upon enrollment, a typical mean value for COPD studies at our center with similar enrollment criteria. These two between-group calculations (a and b) assume a two-sided two-group t test. ^cThis is a conservative estimate based on extensive experience in NPD; within group SD is < 3 at our center. ^dBased on experience testing ivacaftor in CF patients, LCI exhibits even greater power than spirometry, so we have an excellent sample size to detect a meaningful effect.²⁸

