9.1 Role of Vertex IIS regarding provision of study drug and placebo

- Vertex Pharmaceuticals will provide ivacaftor and matching placebo to randomize up to approximately 50 subjects to achieve approximately 40 completers (35 active patients and 15 placebo treated patients for 84 days, assuming 5 dropouts in the ivacaftor group and 5 dropouts in the placebo group). This will provide sufficient compound for lost samples, if they occur.

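### Number randomised, allocation ratio and drop-out are stated incompatibly, and the between-group power in Table 2 footnotes a and b does not match any arm sizes the documents give

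*Combined protocol and SAP*

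**What the plan says.** **Number randomised.** The synopsis (General Description) says "Approximately 40 subjects with COPD will be randomized". Section 4.0 says "Patients will be randomized 3:1 to active drug (n=30) and placebo (10"), which is also 40. The next list in Section 4.0 plans "to randomize up to 50 subjects to achieve 40 completed subjects" and attaches the same 30 and 10 to that statement.

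**Ratio.** The synopsis and Section 4.0 both give 3:1 as the randomisation ratio. The supply paragraph, which appears in the synopsis (Role of Vertex IIS) and again in Section 9.1, provides drug "to randomize up to approximately 50 subjects to achieve approximately 40 completers" and splits the 50 as "35 active patients and 15 placebo treated patients for 84 days".

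**Drop-out.** The same supply paragraph continues "assuming 5 dropouts in the ivacaftor group and 5 dropouts in the placebo group". The Table 2 legend in Section 6.1 uses 27 active patients, "accounting for 10% drop-out rate".

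**Power.** Section 6.1 bases the trial's size on within-subject change in MCC and FEV1, and Table 2 is built on a two-sided paired t-test with alpha 0.05. Footnotes a and b add between-group power from a two-sided two-group t-test:
- sweat chloride: 80% at SD 12.8 and 90% at SD 11.1 mmol/L;
- FEV1: 80% for 3.9 percentage points.

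Neither footnote gives a placebo number, and footnote b gives no SD.

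**The concern.** Thirty active patients is the randomised number in one sentence of Section 4.0 and in Table 2 (30 less 10% is 27). It is the completing number in the next part of Section 4.0 and in the supply paragraphs (35 less 5 is 30). The randomisation list, the drug order and the power table therefore rest on different designs.

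The statistical stake lies in the comparison with placebo. Section 6.0 plans between-group tests as secondary analyses, and FEV1 is one of the two main efficacy outcomes. In a 3:1 trial the small placebo arm largely determines the precision of that comparison. A power figure that states no placebo number cannot be tied to the design, and a reader would take 80% or 90% at face value.

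**Working it through.** **1. The counts side by side**

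| Place | Randomised | Completing or analysed | Ratio at randomisation | Drop-out |
|---|---|---|---|---|
| Synopsis; Section 4.0, first statement | about 40 (30:10) | not given | 3:1 | not given |
| Section 4.0, later statement | up to 50 | 40 (30:10) | not given | 10/50 = 20% at the ceiling |
| Synopsis and Section 9.1, supply | 35:15 | 30:10 (35−5, 15−5) | 35/15 = 2.33:1 | 5/35 = 14.3%; 5/15 = 33.3% |
| Table 2 | 30 active (27/0.9) | 27 active | not given | 10% |

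The 14.3% and 33.3% are derived, not printed. A 3:1 split of 50 would be 37.5:12.5. Applying Table 2's 10% to 35 active gives 31.5, not 27.

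**2. Reproducing the within-subject entries**

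The paired t-test has noncentrality δ√n/SD and n−1 degrees of freedom, with two-sided alpha 0.05. SDs are from Table 2: MCC 7, FEV1 5, sweat chloride 4. For FEV1 at n=27, 2.8 × √27 / 5 = 2.91 against a critical t of 2.056 gives power 80%.

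| Endpoint | Stated (80% / 90%) | n=27 | n=30 |
|---|---|---|---|
| MCC | 3.9 / 4.5 | 3.92 / 4.54 | 3.70 / 4.29 |
| FEV1 | 2.8 / 3.2 | 2.80 / 3.24 | 2.65 / 3.06 |
| Sweat chloride | 2.3 / 2.6 | 2.24 / 2.59 | 2.12 / 2.45 |

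The entries match at n=27. The one departure is sweat chloride at 80%, which computes to 2.24 and is printed as 2.3 (power at 2.3 is 82%). With 30 completers they improve slightly.

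**3. Reproducing footnotes a and b**

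The two-sample t-test has noncentrality δ / (SD × √(1/n₁ + 1/n₂)) and n₁+n₂−2 degrees of freedom, with two-sided alpha 0.05. The sweat chloride difference is the 9.9 mmol/L in Table 2, and its SDs are those in footnote a. For FEV1 the SD of 5 is an assumption taken from Table 2.

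For FEV1 at 27:27, √(2/27) = 0.272 and 3.9/(5 × 0.272) = 2.87, giving power 80%. At 27:9, √(1/27 + 1/9) = 0.385 and 3.9/(5 × 0.385) = 2.03, giving power 50%.

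| Comparison | Stated | 27:27 | 27:9 | 30:10 |
|---|---|---|---|---|
| FEV1 3.9, SD 5 | 80% | 80.3% | 50.4% | 54.9% |
| Sweat chloride 9.9, SD 12.8 | 80% | 79.6% | 49.7% | 54.2% |
| Sweat chloride 9.9, SD 11.1 | 90% | 89.5% | 61.5% | 66.3% |
| FEV1 difference detectable at 80% | 3.9 | 3.88 | 5.55 | 5.25 |

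Here 27:9 applies Table 2's 10% to both arms of 30:10 (10 × 0.9 = 9), and 30:10 is the completing split. With 27 active patients, the stated powers need about 27 on placebo. A 3:1 design of equal precision would be 54:18, since 1/54 + 1/18 = 2/27. That is 72 analysed patients, more than any total in the documents.

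**The case against.** **The counts can mostly be reconciled.** On the kindest reading, up to 50 are randomised 35:15, 40 complete as 30:10, and 3:1 describes the completers. The total of 40 in the synopsis is then a loose target and 50 a ceiling. This removes much of the 40-versus-50 difference. It does not remove the statement in Section 4.0 that patients are randomised 3:1, since a randomisation list cannot be set by who completes. It also does not fit Table 2, where 30 active patients are the number before drop-out.

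**The sample size calculation is undermined.** A reader might infer this, but the documents do not support it. The trial was sized on within-subject change with an explicit n=27, those entries reproduce, and the other active count (30) improves them slightly.

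**The analysed placebo arm could be anywhere from 9 to 15.** This is also tempting and unsupported. Nine is derived, and 15 is a count before the 5 losses named in the same sentence. The completing number the documents support is about 10. Even 35:15 with no loss gives only 70%, 69% and 81% in the order of the power rows above.

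**Active drug will run out.** A 3:1 list run to 50 needs 37-38 active allocations, and 35 would be reached near patient 47 (35/0.75 = 46.7). That is a worst case. Drug is dispensed in 28-day supplies (Section 11.0), so early drop-outs do not use a full course. Thirty-five courses are 105 supplies, and 37.5 active patients with 5 leaving in the first 28 days would use 32.5 × 3 + 5 = 102.5. At 10% drop-out, 40 completers need about 45 randomised (40/0.9 = 44.4), or about 34 active at 3:1.

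**A smaller SD may have been used.** Dividing each SD by √2 brings 27:9 to 79.5%, 78.8% and 88.9%, close to the stated figures. Footnote a prints its SDs as the between-group values and so gives no basis for this. Footnote b prints none, so for FEV1 the shortfall does rest on SD 5.

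**Reconciling the counts would not cure the footnotes.** This is correct. No arm sizes in the documents reach the stated powers, so the footnotes need their own correction.

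**Conclusion.** The concern holds in a limited form. The randomised total, the ratio and the drop-out assumption are incompatible across the synopsis and Sections 4.0, 6.1 and 9.1, and no single reading satisfies all of them. The within-subject basis for the sample size stands.

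The material numerical error is in footnotes a and b, which match about 27 patients per arm. At 27:9 or 30:10, the two 80% statements become about 50-55% and the 90% statement about 61-66%. The FEV1 difference detectable with 80% power is about 5.2-5.6 points, not 3.9. These figures assume a two-sided two-sample t-test at 0.05 and, for FEV1, SD 5. The between-group tests are secondary analyses in a pilot whose primary outcome is safety, so this should be corrected but does not threaten the design.

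**What to change.** In the synopsis and Sections 4.0, 6.1 and 9.1, state one number randomised, one allocation ratio, one drop-out assumption per arm and the analysed number per arm, labelling each count as randomised or completing. Make the 35:15 supply split agree with the randomisation ratio, or state the ratio it implies.

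Restate footnotes a and b at the actual unequal arm sizes, giving the placebo number and the SD in each. When editing footnote b, also check its relative figure: 3.9/55 is 7.1%, whereas the printed 5.1% corresponds to 2.8/55. The within-subject entries need recalculating only if the analysed active number changes from 27.

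The cost is text and table edits. No extra patients are needed. The downside is a visibly lower between-group power, which the plan should state openly.
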